1.3.3 Rationale for Vitreous Tap and Pharmacodynamic Analysis

A vitreous tap will be performed at the time of diagnosis/IVT injection of drug, and an undiluted vitreous sample as well as aqueous sample will be taken at time of surgery. This will allow for assessment of the cytokine profile before and several days after administration of ONL1204. This will allow for the potential identification of a biomarker for proof of principle of target engagement, via analysis of cytokines and other potential molecular biomarkers that impact visual acuity after surgical repair of retinal detachment. The described procedures are routine for retinal surgeons, with the risk of endophthalmitis thought to be similar to that of IVT injections (1 in 2000-3000 patients).

Page 18 of 52

1.4 Potential Risks and Benefits

1.4.1 Potential Risks of Study Product

There could be a risk of an adverse reaction to the ONL1204 drug product or vehicle.

Although unlikely, potential risks include:

- Intraocular inflammation
- Elevated intraocular pressure
- Visual loss
- Retinal cell death
- Less favorable surgical outcome following repair
- Systemic adverse reaction

Patients will be carefully monitored after vitreous tap and intravitreal injection of ONL1204, with multiple post procedure visits with the investigator. At these visits, visual acuity will be assessed, intraocular pressure measured, the eyes examined according to assessments listed in 6.4.2, and any adverse events (AEs) reviewed. Based on these assessments, additional visits may be scheduled at investigator discretion. This close monitoring for inflammation, infection, and changes in vision will help reduce associated risks.

There is a remote risk of systemic adverse reaction in response to intravitreal injection of ONL1204. This risk is greatly mitigated by the study molecule's long half-life in vitreous (most drug stays in the eye until surgery) and extremely short half-life in plasma. Patients will undergo clinical blood testing, with assessment of complete blood count, renal function tests and hepatic function tests to monitor for any such systemic adverse reactions.

1.4.2 Potential Risk to Fetal Development

Potential risk to fetal development is unknown. Therefore, all female patients of childbearing potential must have a negative pregnancy test before being enrolled in this study, and all participants must use adequate contraceptive precautions during the study, Section 6.4.9.

Page 19 of 52

1.4.3 Potential Risks of Intravitreal Injection, Vitreous Tap, Pupil Dilation and Blood Draw

Intravitreal injection and vitreous tap are common procedures, but both do carry the risk of possible adverse reaction including:

- Infection
- Inflammation
- Irritation
- Pain
- Bleeding
- Increased intraocular pressure
- Retinal holes/retinal tears
- Retinal detachments
- Cataract
- Worsened vision/vision loss/loss of eye
- Corneal abrasion

Pupil dilation is also a common procedure during an eye exam but carries a risk of possible adverse reaction including:

- Redness
- Stinging/discomfort
- Allergic reactions
- Sensitivity to light
- Blurred vision

The procedure of blood draw, even though a common procedure carries the risk of possible adverse reactions such as:

- Pain/discomfort
- Bruising
- Infection
- Fainting

Care will be taken to reduce the risk of infection at the time of the tap and intravitreal injection through antisepsis, sterile technique and expert care as these procedures will be performed by experienced retinal surgeons.

1.4.4 Potential Risks of Vitrectomy

Any surgical intervention has risk, and the risks associated with retinal detachment repair are not insignificant. Patients in this trial, however, will receive the same retinal surgery whether they participate in this trial or not so retinal surgery is not a study specific risk. Potential participants in this study have been diagnosed with macula-off, rhegmatogenous retinal detachment and will be undergoing standard retinal reattachment surgery by means of a pars plana vitrectomy (with or without scleral buckle) and gas tamponade. The surgeon will fully discuss the possible risks of this surgery with the patient prior to the surgery.

1.4.5 Potential Benefit of Study Product

There is a possibility that ONL1204 could prevent photoreceptor cell death, ultimately resulting in better visual acuity in patients treated with ONL1204; however, this is not known.

2 STUDY OBJECTIVE

2.1 Primary Objective

The primary objective will be to determine the Maximum Tolerated Dose (MTD) of ONL1204 and select doses for Phase 2. Determination of this will be through review of the parameters measured in the Schedule of Assessments, as well as adverse event (AE) reports.

2.2 Exploratory Objective

During the study, ocular fluid samples will be collected at the time of study drug injection and at the time of vitrectomy. These samples will be used for pharmacokinetic and pharmacodynamic analyses, the results of which will help inform the dose selection for the Phase 2 trial(s).

3 STUDY ENDPOINTS

3.1 Primary Endpoints

The primary endpoints will be the safety profile demonstrated in this study, including:

- Adverse event reporting
- Clinical evaluations including BCVA
- Clinical laboratory evaluation

3.2 Exploratory Endpoints

The exploratory endpoints will be the pharmacokinetic and pharmacodynamic analyses performed in this study, including:

- Measurement of ONL1204 drug levels in plasma and vitreous fluid for PK analysis
- Cytokine and other potential molecular biomarker measurement in aqueous and vitreous samples, taken by vitreous tap, and at vitrectomy

4 STUDY DESIGN

This proposed study is a single-injection, open-label, dose escalation study to assess the use of intravitreal ONL1204 in patients with macula-off RRD. Approximately 16 patients with RDD will be enrolled. The expected duration of patient participation in the study is approximately 24 weeks (treatment, then 24 weeks of follow-up).

4.1 Overview of Study Design

Sixteen patients will be enrolled in 4 ascending dose groups.

After signing informed consent and meeting all eligibility criteria, patients will undergo a vitreous tap for cytokine and other potential molecular biomarker analysis followed by a single intravitreal injection of ONL1204. This will occur on the day of diagnosis (Day 1). Safety visits will be conducted 1 day post-injection and per Investigator's discretion until Visit 3. At Visit 3 (3+ days post-injection, in accordance with standard of care) patients will undergo surgical repair of their retinal detachment with vitrectomy (with or without scleral buckling) and gas or oil tamponade. At the time of surgery, an undiluted vitreous sample will be collected for pharmacokinetic and pharmacodynamics analyses, and an aqueous sample will be collected for pharmacodynamic analysis. Additional safety visits will be conducted 1 day post-surgery, 14 (+4 days) days post-surgery, Weeks 6, 9 (\pm 7 days each), and Week 24 (\pm 14 days; study exit).

As this is a first-in-human safety study of ONL1204, the first patient in the first cohort will receive the lowest dose of ONL1204. After this patient completes Visit 5 (14 +4 days post-surgery) and a safety review committee reviews the data, the remainder of the patients in that cohort will be enrolled. After all patients in the cohort have completed Visit 5, the SRC will review the available safety data to determine if dose

limiting toxicity exists that prohibits enrolling the next higher dose cohort. This process will be repeated until escalating to the top dose.

The following doses will be evaluated: $25 \ \mu g$, $50 \ \mu g$, $100 \ \mu g$, and $200 \ \mu g$ ONL1204. ONL1204 is available in vials with concentrations of 0.5 mg/mL and 2 mg/mL. Therefore, a volume of 0.05 or 0.1 mL will be injected into the study eye.

Patient participation will be approximately 24 weeks (6 months): a single injection treatment and 24 weeks of follow-up.

4.1.1 Treatment Masking

This is an open-label study and all patients will be receiving study drug.

4.2 Dose Limiting Criteria and Maximum Tolerated Dose

4.2.1 Dose Limiting Criteria

Dose limiting toxicity, if observed, will be declared by the SRC, based on their review of the relevant clinical information.

Determination of dose limiting toxicity will include consideration of the following events:

- 1. Ocular inflammation increases by 2 units from pre-injection on the Standardization of Uveitis Nomenclature (SUN) grading scale for aqueous cell or vitreous haze, secondary to inflammation and not the drug formulation itself, identified post-injection of ONL1204 and prior to retinal reattachment surgery;
- 2. Sustained elevation of IOP characterized as > 30 mmHg for 3 consecutive days, postinjection of ONL1204 and prior to retinal reattachment surgery, despite pharmacologic therapy;
- 3. Reduction in visual acuity from baseline after injection of ONL1204 and prior to retinal reattachment surgery, that in the opinion of the investigator is likely due to the investigational product and results in a:
 - a) Decrease in visual acuity from 20/200 or 20/400 to light perception without progression of the underlying retinal detachment; or
 - b) Decrease in visual acuity from baseline to no light perception.
- 4. Any serious adverse event (SAE) that occurs within the first 14 days following ONL1204 injection that, in the opinion of the investigator, is related to ONL1204.

Page 23 of 52

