4.3 Schedule of Assessments

Table 4-1 Schedule of Study Procedures and Assessments

Study Visit	Visit 1 Day 1 Baseline ² / Injection			Visit 2 Day 2 (¹ ,	Visit 3 (Day 4 +)	Visit 4	Visit 5	Visits 6, 7	Visit 8	Unscheduled Visit(s)
				1 day Post- Injection	3 + days Post- Injection) Day of Surgery (Vitrectomy) ³	1 Day Post- Surgery	14 Days (±4 days) Post- Surgery	Weeks 6, 9 (±7 days)	Week 24 (±14 days) Exit or early termination	
Assessment	Pre- Injection	Study Drug IVT	Post- Injection							
Informed Consent	X									
Medical History	X									
Demographics	X									

³ All Visit 3 procedures are to be performed before vitrectomy.

Note: Screening procedures are in red.

Abbreviations: AE = Adverse event; ETDRS = Early Treatment Diabetic Retinopathy Study; IOP = Intraocular pressure; PK = Pharmacokinetic;

Post-op = Postoperative; OU = Both eyes; SD OCT = Spectral Domain Optical Coherence Tomography; SE = Study eye; UA = Urine analysis.

¹ IOP > 30 mmHg requires consecutive daily visits until resolved or vitrectomy. Visits between visit 2 and 3 may be added per investigator's discretion.

² All baseline procedures to be done before injection, except blood draw for ONL1204 levels and PK sample (may be drawn with clinical laboratory evaluations, and 1 hour [\pm 15 minutes] after injection), and AE reporting, (pre- and post-injection). If injection is scheduled for early morning, baseline procedures can be done the day before surgery.

Page 25 of 52

Study Visit	Visit 1 Day 1			Visit 2 Day 2 (¹ ,	Visit 3 (Day 4 +)	Visit 4	Visit 5	Visits 6, 7	Visit 8	Unscheduled Visit(s)
	Bas	eline ² / Inje	ction	1 day Post- Injection	3 + days Post- Injection) Day of Surgery (Vitrectomy) ³	1 Day Post- Surgery	14 Days (±4 days) Post- Surgery	Weeks 6, 9 (±7 days)	Week 24 (±14 days) Exit or early termination	
Assessment	Pre- Injection	Study Drug IVT	Post- Injection							
Concomitant Medications	X			X	X	Х	X	X	Х	Х
Vital Signs	X			X	Х	Х	X	Х	Х	Х
Height and weight	Х									
Pregnancy Test (UA) (females only)	X								Х	
ETDRS Best Corrected Visual Acuity	OU			OU				OU	OU	SE ⁴
Clinical Laboratory Evaluation	X		X		X				X	

Note: Screening procedures are in red

Abbreviations: AE = Adverse event; ETDRS = Early Treatment Diabetic Retinopathy Study; IOP = Intraocular pressure; PK = Pharmacokinetic; Post-op = Postoperative; OU = Both eyes; SD OCT = Spectral Domain Optical Coherence Tomography; SE = Study eye; UA = Urine analysis. ⁴ OU if clinically indicated.

Page 26 of 52

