For PK concentration data, the number of non-missing values, number of below limit of quantification (BLQ) values, arithmetic mean, standard deviation, median, minimum, maximum, coefficient of variation (CV%), geometric mean and geometric coefficient of variation (geo CV%) values will be presented. For the calculation of summary statistics, unrounded data will be used and reported to three significant figures except for n, n BLQ, and CV% which will be presented to the nearest integer and one decimal place, respectively.

For PK parameters data, the number of non-missing values, arithmetic mean, standard deviation, median, minimum, and maximum values will be presented. Individual PK parameters will be presented to three significant figures except for T_{max} which will be presented to two decimal places.

- Categorical variables: Descriptive statistics will include counts and percentages per category. The denominator in all percentage calculations will be the number of participants in the relevant analysis population with non-missing data, unless specifically stated otherwise. Percentages will be displayed to one decimal place. Proportions will be displayed to 3 decimal places.
- Unscheduled assessments: Only values collected at scheduled study visits/time points will be presented in summary tables. If a repeat assessment was performed, the result from the original assessment will be presented as the result at the specific visit/time point. All collected data will be included in the data listings.

- Assessment windows: All assessments will be included in the data listings and no visit windows will be applied to exclude assessments that were performed outside of the protocol specified procedure windows.
- Result display convention: Results will be center aligned in all summary tables and listings. Participant identifiers visit and parameter labels may be left-aligned if required.
- Date and time display conventions: The following display conventions will be applied in all outputs where dates and/or times are displayed:

Date only: YYYY-MM-DD

Date and time: YYYY-MM-DD HH:MM

If only partial information is available, unknown components of the date or time will be presented as 'NK' (not known), i.e., '2016-NK-NK'. Times will be reported in military time.

Key Definitions

The following definitions will be used:

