13.1.11 Pin Hole Visual Acuity

Pin Hole Visual Acuity measurements (taken at 1 Day Post-Surgery only) will be summarized using descriptive statistics described in section 3.1 for continuous data by cohort by LogMAR Score.

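### Dose-limiting criterion 3 (visual loss between injection and surgery) has one scheduled acuity test in its window and none just before surgery, and 3(a) leaves out the better eligible baselines

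*Protocol*

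**What the plan says.** **The criterion.** Protocol 4.2.1 lists four kinds of event for the SRC. The third is "Reduction in visual acuity from baseline after injection of ONL1204 and prior to retinal reattachment surgery", judged by the investigator as likely due to the product. It has two limbs. Under 3(a), acuity of 20/200 or 20/400 falls to light perception and the detachment has not progressed. Under 3(b), any baseline falls to no light perception. The list is introduced with "Determination of dose limiting toxicity will include consideration of the following events", so it is not closed. Section 10.2 makes these criteria part of each escalation decision.

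**The schedule.** Section 6.4.2 refers to Table 4-1 for timing. The row "ETDRS Best Corrected Visual Acuity" is filled at pre-injection, Visit 2, Visits 6 and 7, Visit 8 and unscheduled visits (study eye). It is blank at Visits 3, 4 and 5. Footnote 3 states: "All Visit 3 procedures are to be performed before vitrectomy". Pin-hole acuity appears only at Visit 4, and SAP 13.1.11 agrees. Low-luminance and low-contrast acuity begin at Visit 6.

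**Extra visits.** Footnote 1 has one mandatory trigger: "IOP > 30 mmHg requires consecutive daily visits until resolved or vitrectomy". Otherwise, "Visits between visit 2 and 3 may be added per investigator's discretion".

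**Eligibility.** Inclusion criterion 4 (Protocol 5.2) accepts study-eye acuity from 20/100 down to hand motion.

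**Reporting.** SAP section 3 says: "Only values collected at scheduled study visits/time points will be presented in summary tables". Unscheduled results go to listings.

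**The concern.** A dose-limiting criterion works only if the measurement it depends on is taken while the criterion applies. Criterion 3 runs up to surgery. Section 1.4.1 says most of the drug stays in the eye until then, so exposure continues through days on which no acuity test is scheduled. A patient whose pressure stays at or below 30 mmHg and who has no discretionary visit goes to surgery with acuity last measured on Day 2.

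The gap cannot be filled afterwards. A pin-hole value taken after vitrectomy and tamponade does not show what the eye saw the day before. The SRC clears the sentinel patient and then the cohort after Visit 5. For a patient with no extra visits, its scheduled acuity data by then are the baseline, Day 2 and one post-operative pin-hole value. A dose-limiting toxicity makes the next lower dose the MTD, and determining the MTD is the primary objective.

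The wording of 3(a) raises a second problem. It names two baselines and leaves out the better ones that eligibility admits. The rule as written therefore captures a smaller loss and misses a larger one with the same end state.

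**Working it through.** The plan states no figure to reproduce. The check sets the schedule against the window, then 3(a) against eligibility.

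**Reading the table.** The BCVA row is intact in the text version. It has the same ten columns as the complete vital-signs row, so the blank at Visit 3 is part of the schedule. The pressure, slit-lamp and ophthalmoscopy rows are scrambled and cannot be placed by column. Nothing below depends on them.

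**Acuity tests in the window.** Scheduled after injection and before surgery: Visit 2 = 1, Visit 3 = 0, total 1.

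**Elapsed time.** Let surgery be *T* days after injection. Table 4-1 gives *T* of at least 3, with no upper limit. Section 1.2.1 plans surgery within 7 days. The Day 2 test is 1 day after injection.

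- Day 2 test to surgery: *T* − 1, which is 3 − 1 = 2 days to 7 − 1 = 6 days.
- Day 2 test to pin-hole acuity: (*T* + 1) − 1, which is 3 to 7 days.
- The next scheduled ETDRS BCVA is at Week 6.

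These are elapsed times. They are not shares of risk or of missed events.

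**Baselines and 3(a).** For Snellen values, logMAR = log10(denominator/20). SAP 13.1.5 gives logMAR = −0.02 × letters + 1.7, so letters = (1.7 − logMAR)/0.02. It sets count fingers at 2.0, hand motion at 3.0 and light perception at 3.9. The loss to light perception is 3.9 minus the baseline.

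| Eligible baseline | logMAR | Letters (approx.) | Loss to light perception | Named in 3(a) |
|---|---|---|---|---|
| 20/100 | 0.70 | 50 | 3.2 | no |
| 20/125 | 0.80 | 45 | 3.1 | no |
| 20/160 | 0.90 | 40 | 3.0 | no |
| 20/200 | 1.00 | 35 | 2.9 | yes |
| 20/400 | 1.30 | 20 | 2.6 | yes |
| Count fingers | 2.0 | off chart | 1.9 | no |
| Hand motion | 3.0 | off chart | 0.9 | no |

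Eligible baselines better than 20/200 are the letter scores 36 to 50, which is 50 − 36 + 1 = 15 scores. From each of them, a fall to light perception exceeds the 2.9 logMAR loss that 3(a) counts from 20/200. None meets 3(a), and 3(b) needs no light perception. Read literally, 3(a) also omits baselines between 20/200 and 20/400.

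**The case against.** The best defence is that criterion 3 concerns gross loss. A fall to light perception needs no refracted letter score to detect, adverse events are collected at Visit 3 before vitrectomy, and section 7.11 counts decreased acuity as an adverse event. Discretionary visits include study-eye BCVA. Section 1.4.1 says in general terms that acuity is assessed at post-procedure visits. The SRC's list is open. A related loss could qualify as a serious adverse event under criterion 4, and with surgery by day 7 any such loss falls within that criterion's 14 days. In cohorts of four, listings show every patient, and the SRC does not decide from final summary tables.

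Much of this stands. It is why the finding is a gap in the criterion and not a failure of it, and why the SAP point is secondary. It does not remove the finding:

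- **Adverse events.** The loss must first be measured or noticed, in an eye that has already lost central vision. The SRC can weigh only the data it has.
- **Extra visits.** Only raised pressure makes them mandatory. Visual loss does not.
- **Section 1.4.1.** It names no visit, and section 6.4.2 leaves timing to Table 4-1. It supports adding the test but does not schedule it.
- **Criterion 4.** It depends on a judgement of seriousness. A 20/200 baseline would meet 3(a) without that step.

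It can also be said that extending 3(a) to 20/400 or better still omits count fingers and hand motion. That is so. Their falls to light perception (1.9 and 0.9 logMAR) are smaller than the 2.6 at the sponsor's own lower bound, so keeping that bound is coherent. 3(b) still covers those patients.

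The SRC charter and the manual of procedures are not available here, and either could address these points.

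**Conclusion.** Both parts hold and should be fixed. The criterion 3 window contains one scheduled post-injection acuity test, on Day 2, and the last 2 to 6 days before surgery contain none. That range assumes surgery 3 to 7 days after injection; later surgery, which Table 4-1 permits, lengthens it. Limb 3(a) leaves out 15 eligible letter scores better than 20/200, from which a fall to light perception is a larger loss than from either named baseline.

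The documents do not say how many patients would have such baselines, and they give no basis for estimating how often a qualifying loss would be missed. The SRC's discretion, adverse-event reporting and criterion 4 remain as partial safeguards. In the final report, Day 2 will be the only post-injection BCVA within the window to appear in summary tables.

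**What to change.** 1. **Table 4-1.** Add study-eye visual acuity to the Visit 3 column. Footnote 3 already places Visit 3 procedures before vitrectomy. Scheduled post-injection tests in the window rise from 1 to 2, the gap before surgery closes, and the schedule then matches section 1.4.1.
2. **Criterion 3(a).** Replace the two named starting acuities with a baseline of 20/400 or better. Keep the end state and the condition on the detachment as they are.

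The cost is a protocol amendment and one short, non-invasive test at an existing visit. Section 6.4.2 specifies ETDRS BCVA at 3 metres, and the documents do not say whether that set-up is available where surgery takes place. If it is not, an off-chart check is enough for this criterion, because SAP 13.1.5 treats light perception and no light perception as off-chart results.

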4.2.2 Dose Escalation Decisions

Dose escalation decisions include the following:

- 1. To begin enrolling the next cohort at the planned dose or an adjusted dose.
- 2. To delay opening the next cohort in order to collect additional safety on the current cohort, or to enrol additional patients in the current cohort if safety concerns are identified.
- 3. To stop the cohort escalation if unacceptable toxicities are noted.

If, in the opinion of SRC, dose limiting toxicity is reached, the previous, lower dose will be considered the Maximum Tolerated Dose (MTD).

4.3 Schedule of Assessments

Table 4-1 Schedule of Study Procedures and Assessments

Study Visit	Visit 1 Day 1 Baseline ² / Injection			Visit 2 Day 2 (¹ ,	Visit 3 (Day 4 +)	Visit 4	Visit 5	Visits 6, 7	Visit 8	Unscheduled Visit(s)
				1 day Post- Injection	3 + days Post- Injection) Day of Surgery (Vitrectomy) ³	1 Day Post- Surgery	14 Days (±4 days) Post- Surgery	Weeks 6, 9 (±7 days)	Week 24 (±14 days) Exit or early termination	
Assessment	Pre- Injection	Study Drug IVT	Post- Injection							
Informed Consent	X									
Medical History	X									
Demographics	X									

³ All Visit 3 procedures are to be performed before vitrectomy.

Note: Screening procedures are in red.

Abbreviations: AE = Adverse event; ETDRS = Early Treatment Diabetic Retinopathy Study; IOP = Intraocular pressure; PK = Pharmacokinetic;

Post-op = Postoperative; OU = Both eyes; SD OCT = Spectral Domain Optical Coherence Tomography; SE = Study eye; UA = Urine analysis.

¹ IOP > 30 mmHg requires consecutive daily visits until resolved or vitrectomy. Visits between visit 2 and 3 may be added per investigator's discretion.

² All baseline procedures to be done before injection, except blood draw for ONL1204 levels and PK sample (may be drawn with clinical laboratory evaluations, and 1 hour [\pm 15 minutes] after injection), and AE reporting, (pre- and post-injection). If injection is scheduled for early morning, baseline procedures can be done the day before surgery.

Page 25 of 52

Study Visit	Visit 1 Day 1			Visit 2 Day 2 (¹ ,	Visit 3 (Day 4 +)	Visit 4	Visit 5	Visits 6, 7	Visit 8	Unscheduled Visit(s)
	Bas	eline ² / Inje	ction	1 day Post- Injection	3 + days Post- Injection) Day of Surgery (Vitrectomy) ³	1 Day Post- Surgery	14 Days (±4 days) Post- Surgery	Weeks 6, 9 (±7 days)	Week 24 (±14 days) Exit or early termination	
Assessment	Pre- Injection	Study Drug IVT	Post- Injection							
Concomitant Medications	X			X	X	Х	X	X	Х	Х
Vital Signs	X			X	Х	Х	X	Х	Х	Х
Height and weight	Х									
Pregnancy Test (UA) (females only)	X								Х	
ETDRS Best Corrected Visual Acuity	OU			OU				OU	OU	SE ⁴
Clinical Laboratory Evaluation	X		X		X				X	

Note: Screening procedures are in red

Abbreviations: AE = Adverse event; ETDRS = Early Treatment Diabetic Retinopathy Study; IOP = Intraocular pressure; PK = Pharmacokinetic; Post-op = Postoperative; OU = Both eyes; SD OCT = Spectral Domain Optical Coherence Tomography; SE = Study eye; UA = Urine analysis. ⁴ OU if clinically indicated.

Page 26 of 52

Study Visit	Visit 1 Day 1 Baseline ² / Injection			Visit 2 Day 2 (¹ ,	Visit 3 (Day 4 +)	Visit 4	Visit 5	Visits 6, 7	Visit 8	Unscheduled Visit(s)
				1 day Post- Injection	3 + days Post- Injection) Day of Surgery (Vitrectomy) ³	1 Day Post- Surgery	14 Days (±4 days) Post- Surgery	Weeks 6, 9 (±7 days)	Week 24 (±14 days) Exit or early termination	
Assessment	Pre- Injection	Study Drug IVT	Post- Injection							
Blood Sampling for Plasma ONL1204 PK			X ⁵	X	X		X	X ⁶	X	
Study Drug IVT		X								
Pin Hole Visual Acuity						OU				
Low Luminance ETDRS Best Corrected Visual Acuity								OU	OU	
Low Contrast ETDRS Best Corrected Visual Acuity								OU	OU	
Contrast Sensitivity Testing								OU	OU	
Farnsworth D15 Color vision test									OU	

⁵ Post-injection blood sample for plasma PK to be drawn 1 hour (\pm 15 minutes) after study drug IVT. ⁶ Blood sample for plasma PK to be drawn only on Visit 7 (week 9)

Page 27 of 52

Study Visit Visit 1 Visit 2 Visit 3 Visit 4 Visit 5 Visits 6, 7 Unscheduled Visit 8 Day 2 (¹, Day 1 (Day 4 +) Visit(s) Baseline²/ Injection 3 + days Post-1 day 1 Day Post-Week 24 14 Days Weeks 6, 9 (±7 Injection) (±14 days) Post-Surgery (±4 days) days) Injection Day of Post-Exit or early Surgery Surgery termination (Vitrectomy)³ Pre-Study Post-Assessment Injection Drug Injection IVT Intraocular SE⁴ OU OU SE OU OU OU OU Pressure⁷ Slit Lamp SE⁴ OU OU OU SE OU OU Biomicroscopy Indirect SE⁴ OU OU OU SE OU OU Ophthalmoscopy Fundus OU OU Photography **ONL1204** Fundus OU Autofluorescence B Scan SE Ultrasonography (optional) SD OCT OU OU SE SE

Note: Screening procedures are in red

Abbreviations: AE = Adverse event; ETDRS = Early Treatment Diabetic Retinopathy Study; IOP = Intraocular pressure; PK = Pharmacokinetic;

Post-op = Postoperative; OU = Both eyes; SD OCT = Spectral Domain Optical Coherence Tomography; SE = Study eye; UA = Urine analysis.

⁷ iCare Tonometry and Tonopen methods of measurement are acceptable.

Page 28 of 52

Study Visit	Visit 1 Day 1			Visit 2 Day 2 (¹ ,	Visit 3 (Day 4 +)	Visit 4	Visit 5	Visits 6, 7	Visit 8	Unscheduled Visit(s)
	Baseline ² / Injection			1 day Post- Injection	3 + days Post- Injection) Day of Surgery (Vitrectomy) ³	1 Day Post- Surgery	14 Days (±4 days) Post- Surgery	Weeks 6, 9 (±7 days)	Week 24 (±14 days) Exit or early termination	
Assessment	Pre- Injection	Study Drug IVT	Post- Injection							
Vitreous Tap for Cytokine / Biomarker Analysis	SE									
Undiluted Vitreous Collection for Cytokine / Biomarker Analysis and ONL1204 Drug Levels					SE					
Anterior Chamber Tap for Cytokine / Biomarker Analysis					SE					
Adverse Events	X		Х	X	Х	Х	Х	X	Х	Х

Note: Screening procedures are in red

Abbreviations: AE = Adverse event; ETDRS = Early Treatment Diabetic Retinopathy Study; IOP = Intraocular pressure; PK = Pharmacokinetic; Post-op = Postoperative; OU = Both eyes; SD OCT = Spectral Domain Optical Coherence Tomography; SE = Study eye; UA = Urine analysis.

